5 STUDY POPULATION

The study will enroll subjects who meet all inclusion and none of the exclusion criteria and those subjects who are expected to comply with the protocol. The study is expected to enroll about 21 subjects, and possibly more based on pre-specified dose escalation criteria.

5.1 INCLUSION CRITERIA

ARDS Cohort only:

1. Patient maintains a diagnosis of ARDS according to the Berlin definition of ARDS (See Appendix C).⁵ All four components of Berlin criteria must be satisfied at Screening:
 - a. Acute onset of respiratory failure within 1 week of a known clinical insult or new or worsening respiratory symptoms
 - b. Respiratory failure associated with known ARDS risk factors and not fully explained by either cardiac failure or fluid overload (an objective assessment of cardiac failure or fluid overload is needed if no risk factors for ARDS are present)
 - c. Radiological abnormalities on chest X-ray or on computed tomography (CT) scan, i.e., bilateral opacities that are not fully explained by effusions, nodules, masses, or lobar/lung collapse
 - d. Hypoxemia with $\text{PaO}_2/\text{FiO}_2 \leq 300$ mmHg (40 kPa) and positive end expiratory pressure (PEEP) ≥ 5 cm H₂O (the $\text{PaO}_2/\text{FiO}_2$ may be estimated from pulse oximetry or determined by arterial blood gas; PEEP requirement may also be established by noninvasive ventilation, or high-flow nasal canula at ≥ 30 L/min)
2. The radiological and hypoxemia criteria (1c and 1d) must occur within the same 24-hour period. The time of onset of ARDS is when the last of the two specified ARDS criteria is met.
3. Administration of the first dose of study product must be planned to take place within 14 days of ARDS diagnosis.

PNA Cohort only:

4. Patient is diagnosed with pneumonia based on defined as pulmonary infiltrate on chest radiography not seen previously plus at least 1 symptom compatible with pneumonia, such as cough, fever, dyspnea, and/or chest pain.
5. Pneumonia is severe per 2019 ATS/IDSA criteria (See Appendix C)⁶.
6. Patient is on appropriate antibiotic therapy, in the opinion of the investigator.

Both cohorts:

7. An informed consent from the patient or the patient's legal representative must be available.
8. Patient is aged ≥ 18 years.

5.2 EXCLUSION CRITERIA

An individual who meets any of the following criteria will be excluded from participation in this study:

1. Patient is in moribund state with expected survival < 24 hours.
2. Patient is pregnant.
3. Patient has baseline clinical morbidity that, in the opinion of the Investigator, would prevent patient from coming off ventilation, e.g., motor neuron disease, Duchenne muscular dystrophy, or rapidly progressive interstitial pulmonary fibrosis.

[figure not shown]
4. Patient has severe baseline (prior to diagnosis of ARDS or PNA) vital organ dysfunction defined as:
 - a. New York Heart Association Class IV heart failure
 - b. End-stage renal failure requiring dialysis
 - c. Severe liver failure (Child-Pugh C)
 - d. Pulmonary disease requiring home oxygen.
5. Patient is currently enrolled into another therapeutic clinical trial with an experimental therapy that has not received marketing approval by U.S. FDA. Note: therapies that have received emergency approval for COVID-19 by U.S. FDA are not an exclusion criterion.
6. Patient received previous MSC-based therapy.
7. Patient has history of sensitivity to heparin, such as allergy or heparin-induced thrombocytopenia.
8. Major trauma in the preceding 5 days.
9. Burn injury on more than 15% of the body.
10. PNA Cohort only: etiology of severe pneumonia is known or suspected to be obstructive (i.e. due to cancer) or fungal.

5.3 SCREEN FAILURES

[figure not shown]
Screen failures are defined as subjects who consent to participate in the clinical study but never receive Descartes-30 cells. A minimal set of screen failure information is required including demography and screen failure details. Screen failure data will not be recorded within the Case Report Form (CRF).

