7.1.2 DOSING AND ADMINISTRATION

7.1.2.1 PRE-INFUSION MONITORING AND DELAY OF CELL INFUSION

[figure not shown]
Infusions can be delayed up to 96 hours based on PI discretion. Prior to all Descartes-30 infusions, patients should be observed for 2 hours (\pm 30 min) to document their stability by meeting the following parameters and based on PI's best clinical judgement:

1. Patient is not requiring a change in ventilator settings
2. Stable use of vasopressors if the patient required vasopressors for blood pressure support.
Stable use is defined as increasing no more than 50% of baseline recorded at initiation of monitoring.

During 2-hour monitoring, following parameters should be recorded at least every 30 min: ventilation variables [type of ventilation (CPAP, BiPAP, or intubation), ventilation rate, pulse, tidal volume, positive end-expiratory pressure (PEEP)], recording of vasoactive drugs and renal support and vital signs [include core temperature, mean arterial pressure (mmHg), pulse (beats/min), respiratory rate (breaths/min)]. If patients do not meet stability criteria for 2 hours, infusion can be delayed for up to 96 hours. If infusion is delayed, the patient will be periodically monitored to assess stability. If infusion is delayed more than 96 hours due to medical instability, patients will come off study treatment. Infusions can also be delayed up to 96 hours in case of a holiday or by PI's discretion.

Patients experiencing toxicities that are probably or definitely related to Descartes-30 will have their next Descartes-30 dose delayed until these toxicities have resolved to at least Grade 2, unless in the documented opinion of the site Principal Investigator and the medical monitor it is reasonable to proceed. During this period, patients will be assessed to record adverse events and decide whether the patient meets criteria for cell infusion. The discussions between the Medical Monitor and site Principal Investigator will be documented. If a dose is delayed for more than 96 hours, the patient will come off study treatment.

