9 STATISTICAL CONSIDERATIONS

9.1 SAMPLE SIZE

As this is an early-phase open-label study with a dose-escalation regimen, no formal sample size calculations have been performed. The sample size has been selected for practical considerations and is based upon experience from similar past clinical study designs. The selected number of subjects is considered sufficient to achieve the clinical study objectives, which are not of an inferential statistical nature.

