16.4.2 DAY 1,2,3

On each day, the following assessments should be completed. There should be at least 12 hours between each assessment. Assessments after Day 1 are omitted if the patient is discharged from ICU.

- Concomitant medications
- Clinical End-point Assessment includes: Survival (Y/N), On mechanical ventilation (Y/N), In ICU (Y/N), In Hospital (Y/N), Use of anti-coagulation (drug, dose, intent: prophylaxis vs therapeutic), WHO Ordinal Score (See Appendix D for scale). If patient is in ICU then the following assessment will be completed: Sequential Organ Failure Assessment (SOFA, See [Appendix B](#) for template form), PaO₂/FiO₂, following ventilation parameters (as applicable): type of ventilation (CPAP, BiPAP, or intubation)/ ventilation rate/ pulse/ tidal volume/ positive end-expiratory pressure (PEEP), recording of vasoactive drugs and renal support, recording of supportive interventions that can impact clinical end-points (use of prone ventilation, use of paralytics, use of pulmonary vasodilators, use of corticosteroids, use of oral decontamination and raising the head of the patient to at least 30° to prevent ventilator-associated pneumonia).
- Research blood collection: All protocol required research blood collection assessments must be conducted in accordance with Laboratory Manual.
- Exploratory Bronchoalveolar lavage: **This should be done only once during this period.** There should be at least 48h passed since the collection for Screening Visit (Section 16.4.1). If BAL can not be performed, then tracheal aspirate.
- CBC with differential: Only if performed as Standard of Care.
- Serum chemistry: Only if performed as Standard of Care. Chemistry includes: Glucose, Ca, Mg, Phos, ALP, Albumin, Total Protein, Total Bilirubin, K, Na, Cl, HCO₃, BUN, Cr, ALT, AST, LDH, Amylase.
- CRP, ferritin, D-Dimer.
- PT/INR, PTT: If performed as Standard of Care.

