16.5 BIOMARKER ANALYSIS AND STATISTICAL CONSIDERATIONS

16.5.1 SAMPLE SIZE

Given the small study size, statistical analyses will be primarily descriptive. Results of Descartes-30 treated patients will be compared to the parallel control patients (one-sided Student's t-test for all continuous variables). Longitudinal analysis of pharmacokinetics and pharmacodynamics biomarkers and will be used to inform (1) additional cohort expansion and/or (2) statistical and power considerations for randomized trial design and inferential statistics.

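### Patients never infused leave the treated group without outcome data, while the visible Appendix E text gives controls no matching gate; this tends to favour Descartes-30 on death-counting and Day 28 outcomes.

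*Combined protocol and SAP*

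**What the plan says.** **Who counts as treated.** Section 5.3: "Screen failures are defined as subjects who consent to participate in the clinical study but never receive Descartes-30 cells". The definition covers any reason for not being infused. Only demography and screen failure details are required, and "Screen failure data will not be recorded within the Case Report Form (CRF").

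**What stands between consent and the first dose.** Section 7.1.2.1 asks for about 2 hours of observation before each infusion, the first included. It looks for no needed change in ventilator settings and for vasopressor use rising by no more than 50%, subject to the investigator's judgement. "If patients do not meet stability criteria for 2 hours, infusion can be delayed for up to 96 hours". Instability beyond 96 hours takes the patient off treatment. These parameters are not eligibility criteria in Sections 5.1 or 5.2.

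**What controls go through.** Section 16.4.1 gives controls an eligibility review. Section 16.4.2 then says: "On each day, the following assessments should be completed. There should be at least 12 hours between each assessment". The visible Sections 16.3 to 16.4.4 contain no stability observation, delay or removal rule.

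**The comparison.** Section 16.5.1: "Results of Descartes-30 treated patients will be compared to the parallel control patients (one-sided Student's t-test for all continuous variables"). No common time origin or entry alignment is visible. The same section says: "Given the small study size, statistical analyses will be primarily descriptive".

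**The concern.** The comparison is meant to show whether treated patients do better than similar untreated patients. As written, the treated group is filtered after consent by something related to outcome. A patient who deteriorates and dies while waiting for the first infusion is not in it; the same patient enrolled as a control is. The treated clock also starts only after the patient has survived the wait and been judged stable. This is selection combined with immortal time, in one group only. Adjusting for screening values would not remove it, because the filter acts after screening.

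The effect could not be measured afterwards, since no outcome is collected in the CRF for those lost. Section 8.2.1 adds to the difficulty. It starts adverse event recording at consent, with entry in the CRF, which does not fit with 5.3, and it starts the SAE reporting period only at first infusion. A death before infusion falls between these rules.

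**Working it through.** **No figure to reproduce.** The plan states no alpha, effect size or control number; Section 9.1 says that "no formal sample size calculations have been performed". What follows measures sensitivity to assumptions.

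**Inputs from the documents.** Treated ARDS patients: 4 dose levels x 3 = 12 in Arm 1, plus 12 in the Arm 2 ARDS Cohort = 24 (synopsis). The 12 PNA patients are left out because Appendix E controls have ARDS.

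**Assumptions.** 12 controls; one-sided 5% level; share never infused q = 5%, 10% or 20%; no drug effect.

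**1. Mortality (descriptive comparison; binary, so outside the t-test).** Let M be Day 28 mortality in all consented patients and m mortality in those never infused. Then treated mortality = (M - q x m)/(1 - q), while controls show M. With M = 30%, q = 10%, m = 100%: (0.30 - 0.10)/0.90 = 22.2%, a false benefit of 7.8 points. With M = 30-40% and m = 80-100%:

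| q | Treated mortality, M = 30% | Treated mortality, M = 40% | False benefit (points) |
|---|---|---|---|
| 5% | 26.3-27.4% | 36.8-37.9% | 2.1-3.7 |
| 10% | 22.2-24.4% | 33.3-35.6% | 4.4-7.8 |
| 20% | 12.5-17.5% | 25.0-30.0% | 10.0-17.5 |

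Milder assumptions give less. With 30% mortality in infused patients and 50-70% in those never infused, the false benefit is q x (0.20 to 0.40): 1.0-2.0, 2.0-4.0 and 4.0-8.0 points.

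**2. Continuous outcomes, one-sided 5% t-test, 24 treated against 12 controls.** Two simulated models.

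- *Normal outcome:* treated N(0,1); a fraction q of controls is worse by d = 1 to 1.5 SD. The mean shift is q x d, from 0.05 x 1 = 0.05 SD to 0.20 x 1.5 = 0.30 SD.
- *Ventilator-free days:* 0 for deaths, uniform on 0-26 for survivors, with the mortality in step 1. The expected shift is 13 x (mortality difference); at M = 30%, q = 10%, m = 100% that is 13 x 0.078 = 1.0 day.

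| q | Normal outcome | Ventilator-free days | Both, rounded |
|---|---|---|---|
| 0 | about 5% | about 5% | 5% |
| 5% | 6.5-7.8% | 5.8-6.5% | 6-8% |
| 10% | 8.8-11.1% | 7.1-9.2% | 7-11% |
| 20% | 14.0-20.3% | 11.1-18.9% | 11-20% |

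With 24 controls, ventilator-free days give 6.0-7.3%, 7.9-11.0% and 12.6-22.9%.

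**3. Change from baseline to 96 hours in survivors.** Two daily severity models with a gate of up to about four days, 24 against 24. When severity regresses to the mean, rejection in favour of Descartes-30 falls below nominal: 1.2-4.4% with a gate on severity level, 2.7-4.8% with a gate on worsening. When deterioration persists, it rises to 7.1-17.7%. The direction is not fixed.

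**4. Does alignment cure it?** In the severity-level model, 24 against 24, ventilator-free days, the unaligned comparison rejects in 6.7-13.2% of trials (3-13% never infused). Giving controls the same gate and time origin brings this to 4.5-5.1%. Counting all consented patients from consent in both groups brings it to 4.9-5.2%.

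**The case against.** **Direction.** A reader might infer that the whole test favours Descartes-30. The documents do not support that. Section 16.5.1 covers all continuous variables, and Section 9.3 lists changes in SOFA and PaO2/FiO2, where the direction can reverse. Section 5.3 also catches patients who withdraw or improve before infusion, and Section 7.1.2.1 allows holiday and discretionary delays. Losing patients who improve would work against the product. This stands and limits the point to outcomes that count death or Day 28 status.

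**Strength of the gate.** It rests on the investigator's judgement, does not require improvement, and can be passed on constant high support. Section 1 allows screening and Day 0 on the same day, and Section 5.2 excludes moribund patients. The share lost may be small. This also stands, but Section 7.1.2.1 itself provides for 96 hours of instability, so the route is open.

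**Missing text.** A reader might infer that controls have no gate at all. The opening of Appendix E was not available, Section 16.5.2 is largely and 16.5.3 wholly blacked out, and the control schedule carries a footnote mark on its screening visit whose text is not among the printed notes. Only the visible text can be said to lack a gate.

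**Consequence.** A reader might infer that this comparison drives cohort expansion and the power of a later trial. Section 16.5.1 attaches those uses to the longitudinal biomarker analysis. The analyses are called primarily descriptive, and the MTD endpoint is unaffected. A descriptive contrast carries the same bias, however, and a one-sided test is still named.

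**Conclusion.** The point holds in limited form. On the visible text, the treated group and its Day 0 are conditioned on reaching the first infusion, and the controls are not. Outcomes that count death or Day 28 status therefore tend to favour Descartes-30 with no drug effect. For change from baseline the direction is uncertain, which is itself a reason to align entry.

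The size is not determinable from the documents. The rejection rates of about 6-8%, 7-11% and 11-20%, against a nominal 5%, rest on assumed shares never infused of 5%, 10% and 20%, an assumed 12 controls and assumed severity in those lost; near 5% the excess is slight. The mortality figures concern the descriptive comparison only. Confidence is medium because part of Appendix E cannot be read. The change is worth making because it is cheap and because the outcome data may not be recoverable later.

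**What to change.** 1. **Section 5.3.** For consented, eligible patients never infused, record in the CRF the reason (death, instability, improvement, withdrawal, other), Day 28 vital status and other chart-based outcomes from the hospital record. List these patients in the report. Reconcile 5.3 with the start of adverse event recording at consent in 8.2.1.
2. **Section 16.5.1, first sensitivity analysis.** Compare mortality and Day 28 chart-based outcomes counting all consented, eligible patients in both groups from consent.
3. **Section 16.5.1, second sensitivity analysis, chart-based outcomes only.** Apply the 7.1.2.1 stability parameters, and the time origin that results, to controls from ICU chart data. Leave the scheduled biomarker sampling days as they are, because moving the control time origin would misalign the Day 1-6 samples.

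Infusion rules and the dosed safety population stay unchanged. The cost is wording in two sections, a short CRF page and chart abstraction. A few controls will drop out of the second sensitivity analysis, and that analysis cannot reproduce holiday or discretionary delays in treated patients.

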5.4 STRATEGIES FOR RECRUITMENT AND RETENTION

Subjects will be identified through inpatient admissions, clinical practices of the investigator or sub-investigators, and through referrals from outside hospitals and physicians.

5.5 PATIENT IDENTIFICATION

6 STUDY PROCEDURES

This section explains the clinical and laboratory tests that will be performed in each study visit. See Section 1 for study visit schedule. Please contact Sponsor for clarification in the event of conflict between Section 6 and Section 1. If applicable, study procedures can be completed remotely.

6.1 SCREENING

All inclusion and exclusion criteria will be reviewed by the Investigator or qualified designee at the Screening Visit to ensure that the subject qualifies for the study. All inclusion criteria must be met and none of the exclusion criteria may apply. Subjects found ineligible during review of inclusion/exclusion will not proceed through the remaining screening process.

- Informed consent
- Demographics, Medical History
- Physical Exams: At minimum should include examination of eyes, mouth, throat, cardiovascular, respiratory, skin, and brief neurological exam.
- Height and weight will be measured and recorded at Screening only, if possible.
- Concomitant medications
- Vital Signs: include core temperature, mean arterial pressure (mmHg), pulse (beats/min), respiratory rate (breaths/min).
 - The same method for assessing temperature should be used at all visits until patient is discharged from the administering unit, if possible.
- CBC with differential: Samples should be taken in the morning between 04:00 and 10:00 using the values closest to 10:00.
- Serum chemistry:
 - Samples should be taken in the morning between 04:00 and 10:00 using the values closest to 10:00.
 - Chemistry includes Glucose, Ca, Mg, Phos, ALP, Albumin, Total Protein, Total Bilirubin, K, Na, Cl, HCO₃, BUN, Cr, ALT, AST, LDH, Amylase.
- Blood and/or sputum culture prior to initiation of antibiotics (required for patients in the PNA Cohort, optional for patients in the ARDS Cohort). If patient is already on antibiotics at the time of screening, blood and/or sputum cultures collected prior to initiation of the antibiotics are acceptable.
- COVID-19 nucleic acid test: A local qualitative sample (e.g., nasopharyngeal swab) if there is clinical suspicion of COVID-19.
- Urinalysis: Samples should be taken in the morning between 04:00 and 10:00 using the values closest to 10:00.
- Pregnancy test: Blood or urine test, only in women with child-bearing potential.
- ECG: Electrocardiogram may be performed as standard of care, at the discretion of the Investigator.
- Research blood collection: All protocol required research blood collection assessments must be conducted in accordance with Laboratory Manual, and the Schedule of Activities. Laboratory requisition forms must be completed, and samples must be clearly labelled with the subject number, protocol number, site number, and visit date. Details for the preparation and shipment of samples will be provided by the laboratory and are detailed in the Laboratory Manual. Reference ranges for all safety parameters will be provided to the site by the laboratory responsible for the assessments.
- Exploratory Bronchoalveolar lavage, Tracheal Aspirate or sputum (induced or expectorated): Optional based on PI's discretion. See Schedule of Activities (Section 1)

and Laboratory Manual for more details. Should be done per institute's standards of operations (alternatively it can be done on Day 0 before infusion)

- Chest Imaging: CT scan or Chest X-Ray (alternatively it can be done on Day 0 before infusion)
- AE review and evaluation: AE collection starts after consent is signed.
- APACHE II Score: See [Appendix A](#) for APACHE II score.
- Clinical End-point Assessment includes: Survival (Y/N), On mechanical ventilation (Y/N), In ICU (Y/N), In Hospital (Y/N), Use of anti-coagulation (drug, dose, intent: prophylaxis vs therapeutic), WHO Ordinal Score (See Appendix D for scale). If patient is in ICU then the following assessment will be completed: Sequential Organ Failure Assessment (SOFA, See [Appendix B](#) for template form), PaO₂/FiO₂, following ventilation parameters (as applicable): type of ventilation (CPAP, BiPAP, or intubation)/ ventilation rate/ pulse/ tidal volume/ positive end-expiratory pressure (PEEP), recording of vasoactive drugs and renal support, recording of supportive interventions that can impact clinical endpoints (use of prone ventilation, use of paralytics, use of pulmonary vasodilators, use of corticosteroids, use of oral decontamination and raising the head of the patient to at least 30° to prevent ventilator-associated pneumonia).

6.2 DAY 0,1,2 DESCARTES-30 INFUSION

Three equal doses will be administered once a day over 3 consecutive days. A minimum of 12 hours should elapse between infusions. Study treatment will be infused intravenously over a period of 30-90 minutes. Further details, including criteria for delaying cell infusion, are available in Section 7 and the Descartes-30 Handling and Storage Manual. Before administration of the product on each infusion day, the following assessments should be completed:

- Physical Exams: At minimum should include examination of eyes, mouth, throat, cardiovascular, respiratory, skin, and brief neurological exam.
- Concomitant medications
- Clinical End-point Assessment includes: Survival (Y/N), On mechanical ventilation (Y/N), In ICU (Y/N), In Hospital (Y/N), Use of anti-coagulation (drug, dose, intent: prophylaxis vs therapeutic), WHO Ordinal Score (See Appendix D for scale). If patient is in ICU then the following assessment will be completed: Sequential Organ Failure Assessment (SOFA, See [Appendix B](#) for template form), PaO₂/FiO₂, following ventilation parameters (as applicable): type of ventilation (CPAP, BiPAP, or intubation)/ ventilation rate/ pulse/ tidal volume/ positive end-expiratory pressure (PEEP), recording of vasoactive drugs and renal support, recording of supportive interventions that can impact clinical endpoints (use of prone ventilation, use of paralytics, use of pulmonary vasodilators, use of corticosteroids, use of oral decontamination and raising the head of the patient to at least 30° to prevent ventilator-associated pneumonia).
- Vital Signs: include core temperature, mean arterial pressure (mmHg), pulse (beats/min), respiratory rate (breaths/min).
 - The same method for assessing temperature should be used at all visits for each individual subject, if possible.
- CBC with differential: Samples should be taken in the morning between 04:00 and 10:00 using the values closest to 10:00. (mandatory for Arm 1, only if done as part of standard of care at institution for Arm 2)
- Serum chemistry (mandatory for Arm 1, only if done as part of standard of care at institution for Arm 2):

- Samples should be taken in the morning between 04:00 and 10:00 using the values closest to 10:00.
- Chemistry includes Glucose, Ca, Mg, Phos, ALP, Albumin, Total Protein, Total Bilirubin, K, Na, Cl, HCO3, BUN, Cr, ALT, AST, LDH, Amylase.
- CRP, ferritin, D-Dimer (mandatory for both Arms)
- Urinalysis: Samples should be taken in the morning between 04:00 and 10:00 using the values closest to 10:00. (mandatory for Arm 1, only if done as part of standard of care at institution for Arm 2)
- ECG: Electrocardiogram may be performed as standard of care, at the discretion of the Investigator.
- Research blood collection: All protocol required research blood collection assessments must be conducted in accordance with Laboratory Manual.
- Chest Imaging: CT scan or Chest X-Ray (Once before first infusion and once between Days 1-6)
- AE review and evaluation
- PT/INR, PTT (mandatory for both Arms)

After completion of Descartes-30 infusion:

1. On Day(s) 0 and 2, Research Blood Collection at 30min (± 10 min). Please See Laboratory Manual for more details.
2. On Day(s) 0 and 2, PT/INR, PTT at 30min (± 10 min).
3. For details of post-infusion clinical monitoring for 4 hours (Arm 1) or 1 hour (Arm 2) after completing infusion, please see Section 7.1.2.3.

